15.0 Risks to Subjects

- IV NAC can cause rate related anaphylactoid reactions in 0.2-18% of patients.^{22,23c} Most of the anaphylactoid reactions are mild (6%) or moderate (10%) with severe reactions (i.e., bronchospasm and hypotension) rare at 1% or less. Bronchospasm more commonly occurs in patients with pre-existing reactive airway diseases, like asthma. Bronchodilating agents are effective in treating these patients. To minimize this risk, patients with asthma, wheezing, or prescribed bronchodilators will be excluded from the study. Similarly, patients with a history of a prior anaphylactoid reactions to acetylcysteine will also be excluded.

If an anaphylactoid events occurs, patients will be treated as described by FDA guidelines.^b IV NAC will be stopped immediately and the patient treated with antihistamine medication (e.g., diphenhydramine) and IV fluids if required. Vasopressors are not typically necessary. NAC therapy may be restarted at a slower rate after resolution of any possible reaction. However, if an anaphylactoid reaction or

similar symptoms return upon reinitiating NAC treatment or increases in severity, IV NAC will be discontinued. Additionally, all possible medication reactions will be reported to the Anesthesia DSMB and MUSC IRB.

There is also a risk of loss of confidentiality.

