6.0 Number of Subjects

Sample size: 70 subjects

First 20 subjects: We will initially randomize 5 patients to each dose group (placebo, 50, 100, and 150 mg/kg) to estimate the dose response curve and to identify the optimal dose. After enrollment of the first 20 patients, the study will undergo review by the study team and statistician.

- If the dose response curve is adequate and the optimal dose identified, 15 additional patients will be randomized to placebo and 15 to the optimal dose to estimate the difference in opioid consumption between patients on placebo vs. the optimal dose. (Total of 50 subjects with 20 from dose response curve and 30 to estimate the difference in opioid consumption.)
- If the dose response curve is not adequate after the initial 20 subjects 5 per each dose group, we will randomize and enroll an additional 5 patients to each dose group (placebo, 50, 100, and 150 mg/kg) to estimate the dose response curve and to identify the optimal dose. Once the optimal dose is identified with these initial 40 patients, 10 additional patients will be randomized to placebo and 10 to the optimal dose to estimate the difference in opioid consumption between patients on placebo vs. the optimal dose. (60 patients total with 40 to create the dose response curve and 20 more to estimate the difference in opioid consumption.)
- A sample size of 20 subjects per group (placebo and optimal dose) allows us to estimate a 95% confidence interval for the mean difference in opioid consumption with a width of ± 0.64 standard deviations from the mean. We will plan to consent 70 subjects to account for withdrawal but will complete the study once 50 or 60 subjects (based on the number of subjects required to create the dose response curve) have completed the protocol.

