10.0 Study Design / Methods

Design: This prospective, double blinded clinical trial will randomize patient to receive placebo (0.45% NaCl or 0.9% NaCl) or NAC (50, 100, or 150 mg/kg). The randomization will be created by a statistician and shared with Investigational Drug Services (IDS) pharmacy prior to patient enrollment.

IDS pharmacy has planned to set up the study to be dispensed from the main OR pharmacy. IDS will prepare numbered kits containing NAC or placebo based on the randomization scheme. The kits will be stored in the OR pharmacy and dispensed based on the assigned subject number. This will allow enrollment any time of day that the OR pharmacy is open.

Groups: Patients will be randomized to receive NAC: 0 mg/kg (placebo; 0.45% NaCl or 0.9% NaCl), 50 mg/kg, 100 mg/kg, and 150 mg/kg (Max dose 15,000 mg). The maximum dose considered will be 150 mg/kg as this has been studied for safety in numerous patient populations including those with severe comorbidities. As NAC may be reconstituted in D5W or 0.45% NaCl, we will reconstitute all NAC doses in 250ml 0.45% NaCl or D5W. We will use 250ml 0.45% NaCl or 0.9% NaCl without NAC as our placebo.

Enrollment:

Following confirmation of informed written consent, patients will be assigned an enrollment number and randomized using the randomization, created by a statistician, to one of four IV NAC groups: 0 mg/kg (placebo; 0.45% NaCl or 0.9% NaCl), 50 mg/kg, 100 mg/kg, or 150 mg/kg. Patients will proceed to the operating room where they will receive general anesthesia for their planned, elective surgical procedure. Intraoperatively, the designated IV NAC or placebo infusion will be initiated and completed by a clinical care team member. Patients will only receive NAC once as a single dose that will run over 60

minutes. Patients will be monitored in the operating room while receiving NAC and in the PACU postoperatively consistent with our standard perioperative care at MUSC.

The recorded anesthesia stop will mark time zero. The primary end point will be 12-hour postoperative opioid consumption.

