14.0 Withdrawal of Subjects (if applicable)

- Circumstances under which subjects will be withdrawn from the research without their consent include severe allergy/intolerance to NAC.
- Subjects may withdraw from the study at any time. If patients voluntarily withdraw from the research study, they will receive our institutional standard of care for perioperative pain management.

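### Sections 14.0 and 15.0 give different outcomes for a first severe reaction that resolves: one requires withdrawal, the other permits a restart of the infusion with no severity limit

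*Protocol*

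**What the plan says.** Three sections of the protocol bear on an infusion interrupted by a reaction.

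- **Section 14.0 (Withdrawal of Subjects)** is mandatory: "Circumstances under which subjects will be withdrawn from the research without their consent include severe allergy/intolerance to NAC". It does not define severe, and it does not mention restarting.
- **Section 15.0 (Risks to Subjects)** first grades the reactions: "Most of the anaphylactoid reactions are mild (6%) or moderate (10%) with severe reactions (i.e., bronchospasm and hypotension) rare at 1% or less". For an anaphylactoid event it then says "IV NAC will be stopped immediately and the patient treated with antihistamine medication (e.g., diphenhydramine) and IV fluids if required", followed by "NAC therapy may be restarted at a slower rate after resolution of any possible reaction". Permanent discontinuation is tied to what happens next: if a reaction or "similar symptoms return upon reinitiating NAC treatment or increases in severity, IV NAC will be discontinued".
- **Section 10.0 (Study Design / Methods)** describes the planned administration: "Patients will only receive NAC once as a single dose that will run over 60" minutes. It states no exception for an interruption.

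Neither Section 14.0 nor Section 15.0 refers to the other. The SAP does not say how a partial or prolonged infusion, or a withdrawn patient, is to be analysed.

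**The concern.** Take a patient whose first reaction is severe and then resolves. A team working from Section 14.0 withdraws that patient. A team working from Section 15.0 may resume the infusion, because the restart permission carries no severity limit and neither trigger for discontinuation (return of symptoms or worsening) has yet occurred. Whether the patient is exposed again then depends on which section is read.

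The stake is mainly patient safety. There is also a smaller effect on the data. The two routes give different received doses and infusion times in a dose-response phase with 5 patients per group. They may also lead to different answers on whether the patient counts towards the 50 or 60 completers in Section 6.0. The protocol does not say whether a withdrawn patient's opioid data are kept.

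**Working it through.** **The rules side by side, by type of reaction**

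| Situation | Section 14.0 | Section 15.0 | Same outcome? |
|---|---|---|---|
| First mild or moderate reaction, resolved | no rule applies | restart permitted | no conflict |
| First severe reaction, resolved | withdrawal required | restart permitted | **conflict** |
| Reaction returns on restart, or worsens | withdrawal if severe | discontinuation required | compatible |

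The conflict sits in the middle row only. The table assumes that severe in Section 14.0 covers what Section 15.0 calls severe (bronchospasm and hypotension). The protocol does not say so, but it offers no other definition.

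**How many patients could fall in that row**

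The protocol states no figure for this, so the count is built from its own inputs.

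- Exposure (Section 6.0): "We will initially randomize 5 patients to each dose group (placebo, 50, 100, and 150 mg/kg"), so three NAC groups of 5 give 15, and 15 more receive the optimal dose in phase 2: 15 + 15 = 30. On the extended path, 3 × 10 = 30 in phase 1 and 10 in phase 2: 30 + 10 = 40.
- Severe rate (Section 15.0): 1% or less.

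Expected number = N × p. Chance of at least one = 1 − (1 − p)^N.

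| Severe rate p | N = 30: expected | N = 30: at least one | N = 40: expected | N = 40: at least one |
|---|---|---|---|---|
| 1% (stated ceiling) | 30 × 0.01 = 0.3 | 1 − 0.99^30 = 26% | 40 × 0.01 = 0.4 | 1 − 0.99^40 = 33% |
| 0.2% (assumed low value) | 30 × 0.002 = 0.06 | 1 − 0.998^30 = 5.8% | 40 × 0.002 = 0.08 | 1 − 0.998^40 = 7.7% |

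The low value is the bottom of the all-grade range in Section 15.0 ("IV NAC can cause rate related anaphylactoid reactions in 0.2-18% of patients"). If the overall rate were that low, severe reactions could be no more frequent.

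**Effect on precision**

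The plan's interval of ±0.64 SD with 20 per group reproduces: t(0.975, 38) × √(1/20 + 1/20) = 0.640. If one optimal-dose patient were lost and not replaced, t(0.975, 37) × √(1/20 + 1/19) = 0.649. The effect on the estimate's precision is negligible, and the point does not rest on it.

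**The 60-minute run (secondary)**

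Suppose the infusion stops at minute s, before 60, and resumes at a fraction r of the planned rate, with r below 1. Delivering the rest takes (60 − s)/r minutes, which exceeds 60 − s. The total, s + pause + (60 − s)/r, therefore exceeds 60 even with no pause. A slower restart either overruns the 60 minutes or leaves the dose incomplete.

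**The case against.** The best defence is that Section 14.0 is mandatory and Section 15.0 only permissive, so a team can obey both by withdrawing severe cases and treating restart as an option for the rest. On that reading there is a missing cross-reference, not a contradiction. It is a sensible reading, but it supplies a severity limit that the text lacks, and the restart sentence is worded to cover every reaction. The defence also notes that Section 15.0 defers to FDA guidelines and Section 13.0 to hospital policy and departmental practice. That stands as a limit: the absence of a severity limit is shown for the protocol's own text only.

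The defence is right about several stronger readings that a reader might infer:

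- *That the rules cannot be applied without unblinding, because they name NAC.* Sections 10.0 and 10.0's account of research procedures use IV NAC as the label for all four arms, including 0 mg/kg. Stopping a blinded infusion needs no knowledge of its contents.
- *That a restart breaks the single-dose wording.* Resuming an interrupted infusion can be read as finishing the same dose. Only the 60-minute duration is at odds with a slower restart.
- *That 5 to 7 patients meet the conflict.* The top all-grade rate gives 30 × 0.18 = 5.4 or 40 × 0.18 = 7.2 reactions, but for mild or moderate ones no withdrawal rule competes with the restart.
- *That a restarted infusion will run into the 12-hour opioid window.* The documents give no operative duration, infusion start time or restart rate, so this cannot be established. Under-delivery, likewise, follows from any safety stop, however well the sections agree.

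**Conclusion.** The point holds for a first severe reaction that resolves: Section 14.0 requires withdrawal, Section 15.0 permits a restart, and nothing in the protocol says which prevails. It most likely touches no patient or one: at the 1% ceiling, 0.3 of 30 expected (0.4 of 40), with a 26% (33%) chance of at least one, and less at lower rates. These are chances of a severe reaction; the conflict also needs the reaction to resolve and a restart to be considered. The mismatch with the 60-minute run is a secondary drafting gap.

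The figures assume that one optimal dose goes into phase 2, that exposure equals the planned number of completers, and that the quoted rates apply to these doses and this setting. The statistical consequence is small. The reason to act is that re-exposure after a severe reaction should not depend on which section is consulted.

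**What to change.** Reconcile Sections 14.0 and 15.0 into one rule for stopping, withdrawing and resuming the infusion, with cross-references and one definition of severe. The content of the rule is for the sponsor's clinicians to decide; none is proposed here. Make the 60-minute wording in Section 10.0 agree with that rule. Record infusion start, stop and restart times and the volume delivered, so that the received dose and its timing are known for any interrupted infusion.

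The cost is a protocol amendment to three paragraphs and a few case report form fields, with no extra patients or procedures.

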16.0 Potential Benefits to Subjects or Others

- IV NAC may provide analgesia with reduced postoperative opioid consumption. This may help reduce postoperative opioid administration for numerous patients undergoing various types of invasive surgical procedures. Because opioid administration is associated with numerous negative side effects, including nausea, vomiting, pruritus, constipation, sedation, and respiratory suppression, reduction in opioid consumption may, in turn, reduce the frequency/severity of these side effects.
- Patients receiving the placebo may receive no direct benefit from participating but will receive current standard care for their surgical procedure.

17.0 Sharing of Results with Subjects

N/A

18.0 Drugs or Devices (if applicable)

N-acetylcysteine (NAC): N-acetylcysteine (NAC) has been an established drug since the 1960s. It is on the World Health Organization's List of 40 Essential Medicines)^a and is an FDA approved medication. NAC is a precursor to the amino acid L-cysteine and the antioxidant glutathione (GSH),² shown to promote homeostatic glutamate regulation by astrocytes. The sulphydryl group (–SH) within the NAC molecule directly scavenges reactive oxygen species (ROS),³ modulates the redox state of the N-methyl-D-aspartate (NMDA) and α -amino-3-hydroxy-5-methyl-4-isoxazolepropionic acid (AMPA) receptors (neurotransmitter effect),⁴ and inhibits the nuclear factor kappa-light-chain-enhancer of activated B cells (NF- κ B) to modulate cytokine synthesis (anti/pro-inflammatory effect).⁵

NAC is probably best known as the treatment for hepatotoxicity from acetaminophen toxicity.^{6b} However, NAC has also been utilized to treat psychiatric disorders (e.g., schizophrenia, obsessive compulsive disorders, addiction, compulsivity, anxiety), neurodegenerative disease symptoms (e.g., Alzheimer's disease, Parkinson's disease), fertility, oral ulcers, chronic pain, hyperglycemia-induced oxidative damage, traumatic brain injury, and numerous other conditions.⁷⁻¹⁶ There are also case reports of NAC helping with improving neurological status in patients comatose with carbon monoxide poisoning.¹⁷ In the perioperative period, NAC has been primarily studied for its anti-inflammatory properties¹⁸ and was noted to reduce the incidence of atrial fibrillation after coronary artery bypass graft surgery.¹⁹ Although NAC has been used in outpatient studies for patients with chronic pain associated with sickle cell anemia²⁰ and diabetic neuropathy,^{14,21} we are not aware of any studies examining NAC to enhance perioperative analgesia and minimize opioid administration.

^a World Health Organization. WHO Model List of Essential Medicines: 20th List. March 2017. Available online: http://www.who.int/medicines/publications/essentialmedicines/20th_EML2017_FINAL_amendedAug2017.pdf?ua=1 (accessed February 24, 2020).

^b FDA. Acetadote (acetylcysteine) Injection Package Insert. Available online: https://www.accessdata.fda.gov/drugsatfda_docs/nda/2004/21-539_Acetadote.cfm (accessed on 22 February 24, 2020).

An IND is not required for this study. First, NAC is FDA approved for IV administration. Next, the doses studied do not exceed the FDA approved doses. Further, this study does not and will not seek to change the FDA labeling. Last, NAC has an over 60-year history of efficacious and safe use. The history of NAC use at the proposed dosages does not suggest a substantial risk or harm to patients.

Pharmacy: NAC is currently stored in the MUSC OR and inpatient pharmacies. It is easily prepared by reconstituting in D5W or 0.45% NaCl. We will reconstitute in 250 ml of D5W or 0.45% NaCl, and 0.45% or 0.9% NaCl will also serve as our placebo. NAC is FDA approved and can currently be ordered by any physician for administration if indicated. Study related NAC will be ordered and administered perioperatively following enrollment. NAC is stable once prepared for 24 hours.

IDS pharmacy has planned to set up the study to be dispensed from the main OR pharmacy. IDS will prepare numbered kits containing NAC or placebo based on the randomization scheme. The kits will be stored in the OR pharmacy and dispensed based on the assigned subject number. This will allow enrollment any time of day that the OR pharmacy is open.

References

3. Radomska-Leśniewska DM SP. N-acetylcysteine as an anti-oxidant and anti-inflammatory drug and its some clinical applications. *Cent J Immunol*. 2012;37(1):57-66.

A pilot trial to determine the effective dose of N-acetylcysteine for opioid reduction in patients undergoing spine surgery.

NCT04562597

Statistical Analysis Plan Date: June 1, 2020

A pilot trial to determine the effective dose of N-acetylcysteine for opioid reduction in patients undergoing spine surgery.

Statistical Analysis Plan

An *a priori* sample size calculation was conducted to determine the precision of the estimated mean difference in opioid consumption at 12-hours between treatment groups in phase 2 for a fixed sample size. A sample size of 20 subjects per group was needed to estimate a 95% confidence interval for the mean difference in opioid consumption with a width of + 0.64 standard deviations from the mean.

The primary outcome of interest in phase 2 was opioid consumption at 12-hours postoperative. Additional opioid outcomes included opioid consumption over time (every 6 hours postoperatively up to 48 hours) and difference in opioid consumption between groups. Mean differences between treatment groups in opioid consumption at different postoperative times, including the primary outcome of 12 hours postoperative, were estimated from a linear mixed model including fixed effects for group, postoperative time, and their interaction and a random patient effect to account for correlation between measures collected on patients over time.

Descriptive statistics were calculated for patient and procedural characteristics across all treatment groups in phases 1 and 2. Additional phase 2 outcomes included time to first PACU opioid rescue dose, PACU VAS pain score, postoperative NRS pain scores, PACU duration, and time to hospital discharge.

Descriptive statistics by treatment group were calculated to allow for comparisons between groups. Average NRS pain score over postoperative time within and between groups was estimated from a linear mixed model including fixed effects for treatment group, postoperative time at pain score measurement, and their interaction as well as a random subject effect to account for correlation between pain scores collected on the same patient over time. Confidence intervals for the median time to first opioid rescue dose was estimated using the Brookmeyer-Crowley approach using the log-log complement transformation.²³ Confidence intervals for the median PACU and hospital length of stay confidence limits are calculated using the distribution free approach described by Hahn and Meeker.²⁴ All analyses were conducted in SAS v. 9.4 (SAS Institute, Cary NC, USA).

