1.0 Objectives / Specific Aims

- Objective: Determine the optimal dose of IV N-acetylcysteine (NAC) to produce opioid reduction following spine surgery and estimate the difference in opioid consumption between placebo and the selected optimal dose.
- The primary outcome will be 12-hour postoperative opioid consumption.
- The secondary outcomes will be 6-hour postoperative opioid consumption.
- Other exploratory outcomes will include intraoperative opioid consumption, postoperative anesthesia care unit (PACU) opioid consumption cumulative, non-opioid analgesic administration, postoperative opioid consumption at additional time points, and VAS pain scores. Patient demographic data, surgical data (procedure, operative duration), preoperative opioid consumption, time to hospital discharge will also be collected.

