4.0 Study Endpoints

- The primary outcome will be 12-hour postoperative opioid consumption.
- The secondary outcome will be 6-hour postoperative opioid pain score.
- Other exploratory outcomes will include intraoperative opioid consumption, postoperative anesthesia care unit (PACU) opioid consumption cumulative, non-opioid analgesic administration, postoperative opioid consumption at additional time points, and VAS pain scores at additional time points.
- Other collected data will include patient demographic data, surgical data (procedure, operative duration), preoperative opioid consumption, time to hospital discharge.

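### The primary 12-hour interval is taken from a 6–48 hour mixed model that pools one variance over all times, so it need not deliver the ±0.64 SD the trial was sized on and will probably be too wide

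*SAP*

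**What the plan says.** The SAP's opening paragraph describes a calculation "to determine the precision of the estimated mean difference in opioid consumption at 12-hours between treatment groups in phase 2", and concludes that 20 per group gives an interval "with a width of + 0.64 standard deviations from the mean". Protocol sections 6.0 and 10.0 give the same figure as ±0.64.

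The SAP's next paragraph names 12-hour consumption as the phase 2 primary outcome and adds "opioid consumption over time (every 6 hours postoperatively up to 48 hours" as a further outcome. Differences at all these times, the 12-hour one included, "were estimated from a linear mixed model including fixed effects for group, postoperative time, and their interaction and a random patient effect".

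The SAP does not state whether each 6-hourly value is a running total or the amount in that interval, whether time is categorical or linear, or any covariance beyond the patient effect. Protocol section 10.0 fixes the origin: "The recorded anesthesia stop will mark time zero". The same section collects opioid data to 48 hours or discharge, so later values may be missing.

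**The concern.** The planned precision and the planned analysis are different calculations. The first uses only the spread of 12-hour values. The second, as written, gives every time point the same variance (patient plus residual) and estimates it from all eight times together. Running totals usually spread out as time passes, so values at 24, 36 and 48 hours inflate the standard error attached to the 12-hour difference.

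The sample size has no justification other than the width of this interval. If the stated model is followed, a reader cannot tell whether the planned precision was reached, and the reported interval may overstate the uncertainty in the primary result.

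**Working it through.** **Inputs from the documents.** 20 per group (SAP; Protocol 6.0 and 10.0); a 95% interval, taken as two-sided; eight times, 6, 12, …, 48 hours (SAP). Neither document gives an SD, a coefficient of variation (CV), a correlation or a pattern of use over time, so everything from step 3 on rests on stated assumptions.

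**1. The plan's figure.** t(0.975, 38) × √(2/20) = 2.0244 × 0.3162 = 0.640. It reproduces as a two-sample t interval on one value per patient. The normal version gives 0.620.

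**2. What the stated model does.** With categorical time and complete data, the fitted 12-hour difference is the raw difference in 12-hour means. Its model-based variance is (2/20) × the mean of the eight time-specific variances. Hence

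half-width = 0.640 × √R, where R = mean variance over the eight times / variance at 12 hours.

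For R = 0.5, 0.8, 1, 1.25, 2 and 3 this gives ±0.45, 0.57, 0.64, 0.72, 0.91 and 1.11 SD. The two calculations agree only at R = 1. (The formula uses 38 degrees of freedom; a Satterthwaite value makes the widths slightly smaller, for example 0.62 at R = 1.)

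**3. Running totals under assumed profiles.** Let the mean 6-hour amount be multiplied by r from one interval to the next. Each amount is scaled by a patient factor (mean 1, CV a) and a within-patient factor (mean 1, CV b). With S = the sum of the first k powers r⁰, r¹, … and Q = the sum of their squares, the variance of the total after k intervals is a²S² + (1 + a²)b²Q.

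- Flat use, a = 1, b = 0.5: the variance is k² + 0.5k. At 12 hours (k = 2) it is 5; the mean over k = 1 to 8 is 25.5 + 2.25 = 27.75. R = 5.55 and the half-width is 0.640 × 2.356 = 1.51.
- Use halving, a = 0.5, b = 1: at 12 hours 0.25 × 2.25 + 1.25 × 1.25 = 2.125; the mean is 2.390. R = 1.125 and the half-width is 0.68.

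Over a and b each 0.5 or 1:

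| r per 6 hours | Half-width (12-hour SDs) |
|---|---|
| 1.0 | 1.19–1.51 |
| 0.9 | 0.99–1.23 |
| 0.8 | 0.86–1.04 |
| 0.7 | 0.77–0.90 |
| 0.6 | 0.71–0.80 |
| 0.5 | 0.68–0.74 |

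In simulation (4,000 trials per setting, gamma data, 20% reduction) the nominal 95% interval covered 96.4–100% of the time. A direct 12-hour t interval covered 94.6–95.9%.

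**4. Discharge before 48 hours.** The stated model was refitted with both CVs at 0.7 and outcome-independent discharge after 18 hours at 0, 15 or 30% per interval (about 110–120 simulated trials per setting, so approximate):

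- flat use: 1.40, 1.16, 0.96;
- use falling 20% per interval: 0.95, 0.86, 0.78;
- use halving: 0.72, 0.68, 0.66.

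The zero-discharge values agree with the formula in step 3 (1.38, 0.96, 0.71).

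**5. Other readings the text leaves open.**

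- Per-interval amounts, categorical time: the variance is proportional to r^(2k). For r from 0.9 to 0.5, √R is 0.71–0.82, so the half-width is ±0.45 to ±0.52 SD and simulated coverage 82–90%, and that for the 6–12 hour amount only. With flat use √R = 1 and there is no mismatch in width.
- Linear time, constant variance, within-patient correlation ρ: the 12-hour variance factor is ρ + (1 − ρ)(1/8 + 15²/1512) = ρ + 0.274(1 − ρ). For ρ = 0.3, 0.5 and 0.8 the half-width is ±0.45, 0.51 and 0.59 SD, valid only if the trend is linear.
- Linear time, running totals: ±0.67 to ±1.37 SD under the step 3 profiles.

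**The case against.** **The covariance is inferred from silence.** The SAP says what the patient effect is for; it does not say that residuals are independent with equal variance. The SAS code may have specified something else. This stands as a limit: the finding concerns the model as written. But a reader who follows the text gets the pooled-variance model.

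**A half-width in SD units is only a planning benchmark.** Using a simple formula ahead of a repeated-measures analysis is common, and ±0.64 is itself correct for a direct 12-hour comparison. That is so. The complaint is that the stated model does not reproduce that precision when variance changes with time.

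**A wide interval is conservative, and the large figures are extreme.** Largely fair. Values near ±1.5 SD need flat use and nobody leaving before 48 hours. With falling use and early discharge the excess can be a few hundredths of an SD.

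**A stronger reading to avoid.** A reader might infer that the direction of the error is unknown, or that the interval under-covers, because the repeated measure is undefined. Protocol 1.0 says "The secondary outcomes will be 6-hour postoperative opioid consumption", Protocol 4.0 says "The secondary outcome will be 6-hour postoperative opioid pain score", and the word cumulative appears only in "postoperative anesthesia care unit (PACU) opioid consumption cumulative". The documents do not support going that far. The conflict over the 6-hour outcome is a separate inconsistency and says nothing about running totals versus intervals. The primary outcome is 12-hour consumption counted from a defined time zero, which most naturally means the 0–12 hour total. Per-interval coding would not yield that outcome at all. Similarly, reporting differences at fixed 6-hourly times suits categorical time better than a fitted line. These readings should be ruled out in the text; they are not the likely case.

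**Conclusion.** The point holds: as written, the primary interval and the precision that justifies the sample size rest on different variances. On the natural reading the interval is too wide: about ±0.68 to ±1.5 SD against ±0.64 under the assumed profiles with complete data, and closer to ±0.64 when patients are discharged early. The point estimate is unaffected provided 12-hour data are complete and time is categorical.

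The mismatch follows from the algebra whenever variance differs between times; its size rests on assumed CVs and use profiles, since the documents supply none. Severity is modest. The trial is a pilot with no test or decision rule attached to this interval, so the harm is a poorly calibrated primary interval and not a wrong decision. The calculations cover only this mismatch; they include no dose-selection step, although phase 1 patients are carried into the final comparison.

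**What to change.** 1. Define the primary outcome as each patient's opioid total from time zero to 12 hours.
2. Make the primary analysis a direct comparison of that total, one value per patient, reported as a mean difference with a 95% t interval. This is the calculation behind ±0.64 SD, and it does not depend on data after 12 hours.
3. Keep the mixed model for the time course. State cumulative coding, categorical time, the degrees-of-freedom method, and a parsimonious covariance that lets variance differ by time, for example heterogeneous compound symmetry. A fully unstructured matrix is a poor default: eight times need 8 × 9 / 2 = 36 parameters from 40 patients, some with missing later values.

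The cost is SAP wording and, since the SAP describes its analyses in the past tense, a short re-run on existing data. No new data are needed.
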